## 12.4 Exploratory Efficacy Analyses

The exploratory efficacy analyses will be conducted in the mITT population with available data per subject. Descriptive statistics will be presented by treatment group and for study eye and qualified fellow eye. Testing of the proportion of subjects who gained  $\geq 15$  letters (3 lines) in BCVA at Week 2, testing of the proportion of subjects who gained  $\geq 10$  letters (2 lines) and  $\geq 5$  letters (1 line) in BCVA at all scheduled visits (ie, Weeks 2, 4, and 8), and testing of the proportion of subjects with complete resolution of epithelial edema (a grade 0 for epithelial edema assessed by biomicroscopy) at all scheduled visits (ie, Weeks 2, 4, and 8) for those who have epithelial edema at Baseline visit (a grade  $> 1$  for epithelial edema assessed by biomicroscopy) will be completed in a similar manner as the secondary endpoints. If there

are less than 5 subjects who have epithelial edema at Baseline visit within each treatment group, no inferential statistics will be produced. Summarization and analysis of the mean change from baseline in corneal thickness including CCT, SCT, TCT, NCT, and ICT as assessed by Pentacam® at all scheduled visits (ie, Weeks 2, 4, and 8), and mean change from baseline in V-FUCHS factor score including glare and diurnal variation (Glare Factor) mean score and visual acuity factor mean score at all scheduled visits (ie, Weeks 2, 4, and 8) will be completed using a similar strategy as for the continuous secondary endpoints.

Robust analysis will be performed on the exploratory efficacy endpoints, the proportion of subjects who gained  $\geq 15$  letters [3 lines],  $\geq 10$  letters [2 lines], or  $\geq 5$  letters [1 line] in BCVA using PP population ODO in similar manner as secondary endpoints. No imputation will be performed on other exploratory efficacy endpoints.

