### 2.1.3 EXPLORATORY ENDPOINTS

- Proportion of subjects who gained  $\geq 15$  letters (3 lines) in BCVA at Week 2
- Proportion of subjects who gained  $\geq 10$  letters (2 lines) in BCVA at Weeks 2, 4, and 8
- Proportion of subjects who gained  $\geq 5$  letters (1 line) in BCVA at Weeks 2, 4, and 8
- Mean change from baseline in CCT as assessed by Pentacam® at Week 4 (selected sites only)
- Mean change from baseline in visual function and corneal health status (V-FUCHS) glare and diurnal variation (Glare Factor) score at Week 4
- Proportion of subjects with complete resolution of epithelial edema at Weeks 4, and 8

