#### 12.1.3 BIOMICROSCOPY

An external magnification and biomicroscopy will be performed using a slit-lamp. Magnification will be consistent with standard clinical practice. The subject will be seated. Examinations of the conjunctiva (hyperemia and edema), cornea (staining, stromal edema, and epithelial edema), anterior chamber (cells and flare), eyelid (erythema and edema), iris/pupil, and lens (lens status and lens opacity for phakic only) will be performed at all scheduled visits for both eyes. The result scoring values are None (0), Mild (+1), Moderate (+2), Severe (+3), and Hypopyon (+4 for anterior chamber cells only). Positive findings will be graded as being clinically significant (CS) and being non-clinically significant (NCS). A "No positive findings" result as collected on the CRF is considered a score value of 0 and NCS. Resolution of corneal edema (a grade of 0 for both stromal edema and epithelial edema) and resolution of epithelial edema (a grade of 0 for epithelial edema) will be identified and analyzed for efficacy.

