### **15. Changes from Protocol-Stated Analyses**

1. Assessment window mapping will be applied for missing values at scheduled visits in the table summaries using ODO.
2. Multiple imputations by FCS regression method instead of protocol-stated monotone regression will be employed to handle missing data without withdrawal or withdrawal due to reasons other than lack of efficacy or adverse events. FCS is a valid statistical method that has greater flexibility than monotone regression method.
3. Additional exploratory efficacy endpoints are added to look at proportion of subjects with complete resolution of epithelial edema at week 4 and 8 among subjects who have epithelial edema at baseline.

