Table 14.2.3.1.2	Proportion of Subjects Who Gained 15 Letters or More in BCVA using ETDRS Method by Visit	Per Protocol Population (Observed Data Only)
Table 14.2.3.2.1	Proportion of Subjects Who Gained 10 Letters or More in BCVA using ETDRS Method by Visit	Modified Intent-to-Treat Population (Observed Data Only)
Table 14.2.3.2.2	Proportion of Subjects Who Gained 10 Letters or More in BCVA using ETDRS Method by Visit	Per Protocol Population (Observed Data Only)
Table 14.2.3.3.1	Proportion of Subjects Who Gained 5 Letters or More in BCVA using ETDRS Method by Visit	Modified Intent-to-Treat Population (Observed Data Only)
Table 14.2.3.3.2	Proportion of Subjects Who Gained 5 Letters or More in BCVA using ETDRS Method by Visit	Per Protocol Population (Observed Data Only)
Table 14.2.4.1	Proportion of Subjects with Complete Resolution of Corneal Edema by Visit	Modified Intent-to-Treat Population (Observed Data Only)
Table 14.2.4.2	Proportion of Subjects with Complete Resolution of Corneal Edema by Visit	Per Protocol Population (Observed Data Only)
Table 14.2.5	Change from Baseline in Central Corneal Thickness ( $\mu\text{m}$ ) as Assessed by Pentacam by Visit	Modified Intent-to-Treat Population (Observed Data Only)
Table 14.2.6	Change from Baseline in V-FUCHS Factor Score by Visit	Modified Intent-to-Treat Population (Observed Data Only)
Table 14.2.7	Proportion of Subjects with Complete Resolution of Epithelial Edema by Visit	Modified Intent-to-Treat Population (Observed Data Only)
Table 14.3.1	Overall Summary of Treatment-Emergent Adverse Events by Treatment Group	Safety Population
Table 14.3.2.1	Ocular Treatment-Emergent Adverse Events by System Organ Class and Preferred Term	Safety Population
Table 14.3.2.2	Non-Ocular Treatment-Emergent Adverse Events by System Organ Class and Preferred Term	Safety Population

Table 14.3.2.3	Ocular Treatment-Emergent Adverse Events Related or Possibly Related to Study Medication by System Organ Class and Preferred Term	Safety Population
Table 14.3.2.4	Non-Ocular Treatment-Emergent Adverse Events Related or Possibly Related to Study Medication by System Organ Class and Preferred Term	Safety Population
Table 14.3.2.5	Serious Treatment-Emergent Adverse Events by System Organ Class and Preferred Term	Safety Population

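### SAP 12.4 defines having epithelial edema at Baseline as grade > 1, which drops every Mild eye and conflicts with the SAP's own grading scale and its Section 15

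*SAP*

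**What the plan says.** SAP Section 12.1.3 sets the biomicroscopy scale: "The result scoring values are None (0), Mild (+1), Moderate (+2), Severe (+3", with +4 reserved for anterior chamber cells. An examination with no positive finding is scored 0. The same section defines "resolution of epithelial edema (a grade of 0 for epithelial edema" as the event to be analysed.

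Section 12.4 restricts that analysis and defines the restriction in parentheses: it is "for those who have epithelial edema at Baseline visit (a grade $> 1$ for epithelial edema assessed by biomicroscopy". It adds that if there "are less than 5 subjects who have epithelial edema at Baseline visit within each treatment group, no inferential statistics will be produced".

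The endpoint is described in three other places:

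- Section 2.1.3: "Proportion of subjects with complete resolution of epithelial edema at Weeks 4, and 8", with no baseline restriction.
- Section 15, which introduces it as an addition to the protocol: "complete resolution of epithelial edema at week 4 and 8 among subjects who have epithelial edema at baseline", with no grade limit.
- Section 18, Table 14.2.7: "Proportion of Subjects with Complete Resolution of Epithelial Edema by Visit", again with no restriction.

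**The concern.** On a scale of 0, 1, 2 and 3, a grade above 1 means Moderate or Severe. An eye graded Mild at Baseline has epithelial edema by the SAP's own scoring, but Section 12.4 treats it as having none. The same grade at a later visit counts as edema that has not resolved. Grade 1 therefore counts as neither present nor absent.

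A programmer who follows Section 12.4 literally will drop all Mild eyes, and nothing in the title of Table 14.2.7 or in Sections 2.1.3 and 15 would tell a reader so. Three things follow:

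- The proportion applies to a more severe subset than its label suggests.
- The denominator shrinks, so the estimate is less precise.
- The fewer-than-5 rule uses the same phrase, so inference is more likely to be withheld.

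The primary CCT endpoint is untouched. So is the secondary corneal-edema resolution endpoint, which has no such cut-off.

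**Working it through.** The SAP states no sample size, power or expected rate for this endpoint, so there is no plan figure to reproduce. The first step is purely textual. The others size the consequence under stated assumptions, because the documents give no baseline grade distribution.

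**1. Which eyes each cut-off admits** (scale from SAP 12.1.3)

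| Cut-off | Grades admitted |
|---|---|
| > 1 (SAP 12.4) | 2 Moderate, 3 Severe |
| >= 1 (any positive finding) | 1 Mild, 2 Moderate, 3 Severe |

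The written rule removes every grade-1 eye and no other eye with edema.

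**2. Reported versus labelled proportion.** Let f be the Mild share among eyes with any epithelial edema, and p_M and p_S the resolution rates in Mild and in Moderate/Severe eyes. The labelled proportion is f × p_M + (1 − f) × p_S; the reported one is p_S. The absolute gap is f × |p_M − p_S|.

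- f = 0.25, difference 10 points: 0.25 × 10 = 2.5 points
- f = 0.50, difference 20 points: 0.50 × 20 = 10 points
- f = 0.75, difference 30 points: 0.75 × 30 = 22.5 points

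For f from 25% to 75% and a difference of 0 to 30 points, the gap runs from 0 to 22.5 points, in either direction.

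**3. The fewer-than-5 rule, with 10 affected eyes per arm.** With 10 eyes of grade >= 1 in each arm (assumed), the rule would not apply under the >= 1 definition. Under > 1, the count per arm is X ~ Binomial(10, 1 − f), arms independent. With q = P(X <= 4), the chance that both arms fall below 5 is q², and that at least one does is 1 − (1 − q)².

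| Mild share f | q | Both arms | At least one arm |
|---|---|---|---|
| 25% | 0.020 | 0.0004 | 0.039 |
| 50% | 0.377 | 0.142 | 0.612 |
| 75% | 0.922 | 0.850 | 0.994 |

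With 15 affected eyes per arm and f = 50%, q = 0.059, giving 0.004 for both arms and 0.115 for at least one.

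**4. The same rule, starting from the planned arm size.** SAP Section 5 gives up to 20 subjects per arm. If a proportion p of these have any epithelial edema (assumed), the eligible count is Binomial(20, p) under >= 1 and Binomial(20, p(1 − f)) under > 1. At p = 60%, the expected denominator falls from 20 × 0.6 = 12 to 9, 6 or 3 for f = 25%, 50% or 75%. The chance that a given arm has fewer than 5 is:

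| p | Under >= 1 | Under > 1, f = 25% | f = 50% | f = 75% |
|---|---|---|---|---|
| 40% | 0.051 | 0.238 | 0.630 | 0.957 |
| 60% | <0.001 | 0.019 | 0.238 | 0.830 |
| 80% | <0.001 | <0.001 | 0.051 | 0.630 |

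**5. Precision.** As an illustration with the observed rate held at 40%, the exact (Clopper-Pearson) 95% interval is 12.2% to 73.8% for 4/10 and 5.3% to 85.3% for 2/5.

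**The case against.** The strongest reply is that entry at Moderate or worse with success at grade 0 is a coherent responder analysis, and that Section 12.4 discloses its cut-off. On this view, Sections 2.1.3 and 15 and the table title are short forms that omit detail; Section 2.1.3 also leaves out the Week 2 visit that Section 12.4 adds. A Mild baseline eye is simply outside the analysis, so nothing is scored inconsistently within one eye. Part of this stands. The difference from Section 15 is that Section 12.4 silently narrows the population; Section 15 states no rival threshold. The direct conflict is with the scale in Section 12.1.3. But if a subset was meant, the SAP never calls it one and gives no reason for it.

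The Mild eyes are also not lost: Section 13.3 plans biomicroscopy shift tables, and a listing gives individual grades. Those tables, however, use the Safety population and, under Section 13, report subjects who switched from QD to BID under BID at Week 8. They do not replace the tested mITT analysis.

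The symbol might have been lost in converting the PDF. That is unlikely, since Section 12.4 prints the greater-than-or-equal sign correctly for the letter gains, but the source file should be checked.

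Finally, the sizes rest on assumed inputs, the largest combine extremes, and the exact intervals are not the planned logistic-model intervals. The endpoint is exploratory and its table is outside the topline set. All of this is true and limits the importance of the point, but it does not make the denominator match its label.

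**Conclusion.** The concern holds. As written, Section 12.4 analyses Moderate and Severe eyes under a phrase that, on the SAP's own scale and in Section 15, covers Mild eyes too. That the cut-off excludes Mild eyes follows from the text and needs no assumption.

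The numerical effect depends on two things the documents do not give: how many eyes are Mild at Baseline, and whether they resolve at a different rate. If no eye is Mild, nothing changes. If the rates are equal, the expected proportion does not shift, but precision is still lost and the fewer-than-5 rule is still more likely to be met. At a Mild share of 25% among 10 affected eyes per arm, the effect on that rule is small (both arms <0.1%, at least one 4%); at 75% it is decisive (85% and 99%).

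The consequence is confined to one exploratory endpoint. It should be corrected, but it does not threaten the trial's main conclusions.

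**What to change.** Check the source file for the symbol and confirm what was intended.

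- **If all eyes with epithelial edema were meant:** change the cut-off in SAP 12.4 to grade >= 1, count the fewer-than-5 rule on that definition, and state the baseline restriction in Section 2.1.3 and in the title or a footnote of Table 14.2.7, so that all agree with Section 15.
- **If a Moderate/Severe subset was meant:** say so in Sections 2.1.3, 12.4 and 15 and in Table 14.2.7.

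While editing, it would help to state whether the fewer-than-5 rule applies when either arm or only when both arms fall short; that is a separate clarification.

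The cost is a few lines of SAP wording and one denominator flag. Grades are already collected at all scheduled visits, so sample size, visits and the primary analysis are unaffected. The change should be made before database lock: in an open-label study, choosing this denominator after outcomes are known would be hard to defend.

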## 12.5 Ad-hoc Efficacy Analyses

If PP population is not exactly the same as mITT population, ad-hoc efficacy tables using mITT population ODO reported as treated may be produced in the same format as efficacy tables using PP population ODO. In the ad-hoc tables, subjects whose dosing regimen was increased from QD to BID starting from Week 4 will be reported under the group “Netarsudil QD to BID” at Week 8 visit. ” If PP population is exactly the same as mITT population, no additional analyses will be performed.

## 13. Safety Analyses

All safety analyses will be conducted using the safety population. For visit-based safety summaries (BCVA, biomicroscopy, IOP, and vital signs), subjects who switched dose group from QD to BID starting from Week 4 will be reported under treatment group BID at Week 8 visit. The baseline value for these subjects will remain the same.

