## 3. Study Design and Procedures

### 3.1 General Study Design and Plan

This is an 8-week, randomized, open-label, multicenter, efficacy and safety study in subjects with FCD.

The study will be conducted at approximately 20 sites in the USA. Two different dosing regimens (QD and BID) of netarsudil will be investigated for their efficacy in reducing or resolving corneal edema in subjects with FCD. Subjects randomized to the netarsudil QD dosing regimen will be instructed to instill one drop of the Study Artificial Tear in their study eye every morning, and one drop of netarsudil in their study eye

every evening. Subjects randomized to the netarsudil BID dosing regimen will instill one drop of netarsudil in their study eye every morning and evening.

CCT will be measured by ultrasound pachymetry at approximately the same time of day  $\pm$  60 minutes and always before noon (local time), at each of the 5 scheduled visits (Screening, Baseline [Day 1], Week 2, Week 4, and Week 8/Exit). In order to be eligible to participate in the study, subjects will have been diagnosed with visually significant central corneal edema due to FCD, in at least one eye, for no longer than 12 months' duration.

At the Screening visit, the subject's diagnosis of FCD will be confirmed and CCT measured using an ultrasonic pachymeter. IOP and BCVA will also be collected.

At the Baseline visit (Day 1), the eligibility assessments conducted during Screening will be repeated to ensure that the subject meets all criteria for enrollment in the study. The same eye must qualify at both the Screening and Baseline visits. If qualified, the subject will be provided with the V-FUCHS patient reported visual disability questionnaire (Wacker 2018). The subject will be randomized (1:1) into the study and provided with study medication. The subject will also be trained on appropriate techniques for applying eye drops.

At the Week 2 and Week 4 visits, the subject will return to the study site for efficacy and safety assessments.

At the Week 4 visit, any subject randomized to netarsudil QD who, in the opinion of the Investigator, has not responded adequately to treatment, may have their netarsudil dosing frequency increased to BID for the remainder of the study. For these subjects, the morning administration of Study Artificial Tear will be terminated.

At the Week 8 visit, a final assessment of efficacy and safety parameters will be conducted, and the subject will exit the study.

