### 4.3 Masking and Unmasking

This is an open-label study, therefore masking and unmasking procedures do not apply.

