### **7.1 Modified Intent-to-Treat (mITT) Population**

The mITT population will include all randomized subjects who have received at least one dose of study medication. This population will be the primary population for efficacy analyses and will be used to summarize a subset of efficacy variables and will summarize subjects as randomized.

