Robustness analysis for secondary efficacy endpoints will be performed using PP population ODO. In the summaries using PP population ODO, subjects whose dosing regimen was increased from QD to BID starting from Week 4 will be reported separately from the subjects who did not change regimens throughout the study duration under a group called "Netarsudil QD to BID" for the Week 8 visit. The baseline value for these subjects will remain the same. At Week 8 visit, comparisons for efficacy endpoints between subjects treated under QD and subjects who switched from QD to BID will be performed as appropriate. However, a high degree of caution should be exerted when interpreting the results as sample sizes might be smaller.

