### 13.1 Adverse Events

An AE is defined as any untoward medical occurrence associated with the use of a drug in humans, whether or not the event is considered drug-related. An AE can therefore be any unfavorable and unintended sign (eg, an abnormal laboratory finding), symptom, or disease occurring after the first dose of study drug, without any judgment about causality. Any pre-existing medical condition that worsens after first administration of the study drug will also be considered a new AE. The AE reporting period starts from the time the subject signs the informed consent until the subject's last study visit. All AEs will be coded using MedDRA Version 23.0.

A treatment-emergent adverse event (TEAE) is defined as any event that occurs or worsens on or after the first dose of study medication. Adverse events recorded on the eCRF which began prior to treatment and remained unchanged or improved will not be included in the summary tables but will be included in the AE data listings. For all AE summary tables, a third group other than QD and BID dose group will be presented to capture the AEs for those subjects who switched the treatment dose from QD to BID starting from Week

4. The AE that began on or after the switch will be considered treatment emergent to the BID treatment; The AE that began before the switch and continued after the switch will be considered treatment emergent to the QD treatment only; if the AE worsened on or after the switch, the new AE (one with higher severity) would become a TEAE for the BID dose and the original AE would be treatment emergent to the QD dose.

An overall summary will be presented that includes the number of events and the number and percentage of subjects who experienced at least one TEAE, by treatment group. This summary will also include breakdowns of TEAEs further categorized as ocular (study eye and fellow eye separately with TEAEs occurred on both eyes counted towards study eye once and fellow eye once) or non-ocular, TEAEs by maximum severity, TEAEs by maximum relationship to study medication, TEAE by expectedness, serious TEAEs, TEAEs leading to study medication discontinuation, TEAEs leading to death.

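### SAP 13 counts QD-to-BID switchers as BID in the Week 8 visit-based safety tables, which tilts BCVA and corneal edema grades against BID

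*SAP*

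**What the plan says.** At Week 4 a subject randomised to QD who, "in the opinion of the Investigator, has not responded adequately to treatment", may move to BID for the rest of the study (SAP 3.1; Protocol 3.1). No objective criterion is given, and SAP 4.3 notes: "This is an open-label study, therefore masking and unmasking procedures do not apply".

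The SAP then handles these subjects in several ways at Week 8:

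- **Visit-based safety tables (SAP 13).** The rule opens "For visit-based safety summaries (BCVA, biomicroscopy, IOP, and vital signs" and continues that "subjects who switched dose group from QD to BID starting from Week 4 will be reported under treatment group BID at Week 8 visit". It adds: "The baseline value for these subjects will remain the same". Ophthalmoscopy is not in the list.
- **AE tables (SAP 13.1).** For switchers, "a third group other than QD and BID dose group will be presented". An AE that began before the switch and simply continued is attributed to QD only.
- **Per-protocol efficacy tables (SAP 12.3).** Switchers "will be reported separately from the subjects who did not change regimens throughout the study duration", in a group called 'Netarsudil QD to BID', with a caution about interpretation. The ad-hoc as-treated tables (SAP 12.5) use the same group.
- **mITT efficacy tables (SAP 7.1).** This population "will summarize subjects as randomized", so switchers stay under QD.

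**The concern.** The switch depends on response. Moving switchers from one column to the other at Week 8 re-sorts subjects by outcome: QD keeps the subjects who did well enough to stay, and BID receives the QD subjects who did not. Because the Day 1 baseline is kept, the switchers' eight-week change, about half of it accrued on QD, is presented as a BID change. A slit-lamp grade increase that arose on QD before Week 4 and persists appears under QD at Week 4 and under BID at Week 8. The AE rule attributes the same kind of event the other way. The BID denominator also grows between Week 4 and Week 8, so its visit-to-visit means describe different people.

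The study is meant to inform later development, and Protocol 3.2 looks for the regimen with the best edema reduction and the fewest adverse effects. A reader who compares the QD and BID columns of the Week 8 BCVA safety table (14.3.3.1) or the biomicroscopy safety tables (14.3.3.2.x) could see a difference that the reporting rule alone produced. Week 8 is also the only post-baseline visit for vital signs.

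**Working it through.** **Plan's own figures.** The documents give no figure for the Week 8 columns, no expected switch rate and no SD for BCVA change. Only the 20 subjects per arm are taken from the sample size section. Its 80% power (effect size 0.577, two-sided alpha 0.10) reproduces as 80.0% by the noncentral t with 19 df, but has no bearing on this point.

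**Set-up.** Suppose the regimens are identical and the extra dose has no effect, so Week 8 BCVA change has the same mean and SD for everyone. A fraction *s* of QD switches, being those with the worst Week 4 response as judged. Let rho be the correlation between that judged response and Week 8 BCVA change; an imprecise judgement, or one based on CCT rather than BCVA, means a lower rho. Let phi be the standard normal density at the *s* quantile. In SD units around the common mean:

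- switchers: -rho·phi/s
- QD stayers: +rho·phi/(1-s)
- BID column (randomised BID plus switchers): -rho·phi/(1+s)
- BID minus QD: -rho·phi·[1/(1+s) + 1/(1-s)] = -2·rho·phi/(1-s²)

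This is negative whenever someone switches and rho is positive, and zero if *s* = 0 or rho = 0.

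**Numbers.** With s = 0.3 and rho = 0.5, phi = 0.348 and the gap is -0.348/0.91 = -0.382 SD. At an assumed SD of 10 letters that is -3.8. Simulation with arms of exactly 20 (100,000 trials per scenario) gives slightly smaller values:

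| Switchers of 20 | rho 0.3 | rho 0.5 | rho 0.7 |
|---|---|---|---|
| 4 | -1.7 | -2.8 | -3.9 |
| 6 | -2.2 | -3.7 | -5.1 |
| 8 | -2.6 | -4.4 | -6.2 |

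Entries are spurious BID minus QD in letters. They scale with the SD: at SD 8 the extremes are 0.8 × -1.7 = about -1.3 and 0.8 × -6.2 = about -5.0.

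**Worked case.** Take 6 switchers, rho 0.5 and an assumed true mean gain of 3.0 letters in both arms. Switchers average -2.55 and QD stayers +5.38 (n = 14). The BID column is (20 × 3.0 + 6 × (-2.55))/26 = 44.7/26 = +1.7 (n = 26). The table would show QD +5.4 against BID +1.7, and BID looks worse in 87% of simulated trials. As randomised, the expected gap is 0 and BID looks worse in 50%.

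**Switchers in their own column.** BID returns to +3.0, but QD is still the selected +5.4, so the gap is -2.4 instead of -3.7. Separation reduces the distortion without removing it.

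**Slit-lamp items** (assumed rates, 6 switchers):

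- *Corneal edema*, 50% in both arms and 80% in switchers (4.8 of 6): QD (10 - 4.8)/14 = 37%; BID (10 + 4.8)/26 = 57%.
- *Hyperemia*, 50% in both arms, but only 30% in switchers (1.8 of 6) if hyperemic eyes are escalated less often: QD (10 - 1.8)/14 = 59%; BID (10 + 1.8)/26 = 45%. The direction reverses, so none can be claimed for items unrelated to response.

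**The case against.** **The safety population is defined as treated** (Protocol 9.4.3; SAP 7.3), and at Week 8 a switcher is using BID. This stands as the rule's rationale. A reader might call the difference between the mITT and safety tables a contradiction, but they are two declared populations. The inconsistency is narrower: the per-protocol population is also as treated, yet it separates switchers, as do the ad-hoc and AE tables. As-treated reporting does not require a subject with four weeks on each regimen to be pooled with subjects on BID throughout.

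**The as-randomised view partly exists.** Tables 14.2.2.1 (BCVA change) and 14.2.4.1 (corneal edema resolution) are planned for the mITT population and marked for topline; no 14.3.3.x table is. This limits the harm. It does not cover the biomicroscopy shift, grade-increase and clinically significant findings tables.

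**The tables are descriptive.** SAP 13.2 to 13.6 plan no between-regimen test, Weeks 2 and 4 are unaffected, and AE summaries have a third group. One might infer that the rule makes BID look worse on all slit-lamp findings, or that it would reverse the sign of the as-randomised comparison. The first does not follow, as the hyperemia case shows. Nothing in the documents establishes the second.

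**The size is assumed.** Escalation is optional and the criterion is the investigator's opinion. If BID truly works better, switchers may recover some ground and the gap would be smaller. That is why a range is given.

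The omission of ophthalmoscopy might be read as a deliberate different treatment. The SAP only leaves it unspecified.

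**Conclusion.** The point holds for response-linked measures. As written, SAP 13 would make BID look worse and QD better at Week 8 on BCVA and on stromal and epithelial edema grades even if the regimens were identical, provided some QD subjects switch and Week 4 response correlates positively with the Week 8 measure. The table above gives the plausible size for BCVA; it rests on an assumed SD, switch rate and correlation and on no effect of escalation. For hyperemia, lids, anterior chamber, lens, IOP and vital signs the BID column mixes two exposure histories, but no direction of bias can be stated. No test or error rate is affected. The change should be made, because the rule produces a misleading display and departs from how the SAP treats the same subjects elsewhere.

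**What to change.** In SAP 13, replace the sentence that places switchers under BID with the following:

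1. At Week 8, visit-based safety tables show switchers in a separate descriptive 'Netarsudil QD to BID' column, giving change from Day 1 and from Week 4. The BID column holds only subjects randomised to BID.
2. The same handling is stated for ophthalmoscopy.
3. A footnote says that the remaining QD column excludes subjects who were escalated for inadequate response, so it is a selected group.
4. A supplementary as-randomised Week 8 summary is added for the BCVA and biomicroscopy safety tables, labelled as supplementary to the as-treated definition in Protocol 9.4.3 and SAP 7.3. It is needed because item 1 alone leaves QD selected.

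The escalation rule, dosing and data collection are untouched. The cost is SAP wording, one extra column of a kind already planned for the AE and per-protocol tables, and a few supplementary summaries; the BCVA one largely overlaps with Table 14.2.2.1 for the study eye. The drawbacks are wider tables and a small n in the switcher column.
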